We designed our analyses based on two study samples. Our main study sample comprised all employees who worked for any duration of time at BJ’s Wholesale Club during the study period. In other words, we included any worker who worked at BJ’s for any length of time during the study period. This is the most inclusive sample.

A potential drawback of these sample inclusion criteria is the possibility of endogenous entry or exit based on the treatment itself. For example, a worker’s decision to join or leave employment at BJ’s Wholesale Club could be a function of the availability of, or exposure to, the wellness program. Therefore, we also defined a relatively stable subsample of employees who were continuously employed at BJ’s in the months before the treatment. This “stably employed” subsample comprised all employees working at BJ’s during, at minimum, the 13 consecutive weeks immediately prior to the onset of the treatment—and thus cannot have entered because of the treatment. Exit from this sample might still be endogenous in theory, however. We will therefore gauge the potential bias introduced by any observed differences in exit between treatment and control sites using a bounding exercise. Additional details on the construction of this subsample are provided below and in the appendix.

B. Balance between treatment and control

We tested balance between treatment and control groups on observable baseline characteristics. We examined balance on demographic variables (age, sex, and race) for all of the analytical samples. We also examined balance on job and employment characteristics in the pre-intervention period for the stably employed subsample, as they by construction were in jobs with characteristics defined prior to the intervention and thus exogenous to the treatment status.

As **Table 8** demonstrates at the employee level, our randomly assigned worksites were balanced on many employee characteristics, but not all. Notably, while treatment and control site workers

⁸ This indicator was our primary definition of participation in our prior phase 1 analysis. Given that we expanded the sample size for phase 2 (with a different total number of modules available), we believe the continuous measure is preferable here.

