The key identifying assumption is that the only mechanism through which being employed in a treatment worksite affects outcomes is through the availability of the wellness program. There are two threats to this assumption. First, to the extent that covariates were not balanced at baseline and those covariates affect the outcomes of interest, that imbalance could bias our estimates. We control for observed covariates and apply weights to balance covariates between treatment and control. Despite these adjustments, unobserved covariates might still be imbalanced.

Second, to the extent that the wellness program affected hiring or tenure of employees, their presence in the data set may be endogenously determined. We address the issue of endogenous entry by pre-specifying a subsample of those who were already employed at the time the intervention began. We defined this more restrictive “stable employment” subsample as comprising employees who had worked continuously for 13 weeks prior to the wellness program. This comes at a cost of reducing the overall sample size. Our goal in choosing the definition for this subsample was to balance the costs and benefits, as detailed in Appendix 2.

In this stably employed subsample, however, exit from the firm's workforce is still potentially endogenous. We deal with this concern in two ways. First, we will test balance on exit between treatment worksites vs. from control worksites overall and for subgroups. Indeed, tenure and time worked are among our primary outcomes. To the extent that we observe any unbalanced exit, we will perform a bounding exercise (assuming that those who exited have outcomes working against any observed effects of the intervention).

D. Subgroup analyses

We pre-specified three subgroup analyses. We selected these subgroups based on differences in key outcomes within the control group for those with different baseline characteristics, such as differences in medical spending by age or in reported exercise by sex (**Table 11**).

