We will analyze how the effect of the wellness program varies along 3 pre-specified dimensions: age (less than 40 years or 40 and above), sex (male or female), and employment status (full-time vs. part-time). In our model, these subgroup analyses are implemented using a set of two-way interaction terms and a triple interaction term. Equation 5 below shows these interaction terms in our ITT framework, using the subgroup analysis on age as the representative equation, where $age40_{it}$ is defined as 1 if the individual is age 40 years or older, and 0 otherwise.

$$\begin{aligned}
 Y_{ijt} = & \beta_0 + \beta_1 TREATMENT_{jt} + \beta_2 TIME_WORKED_{ijt} + \beta_3 Age40_{it} \\
 & + \beta_4 TREATMENT_{jt} * TIME_WORKED_{ijt} + \beta_5 TREATMENT_{jt} * Age40_{it} \\
 & + \beta_6 TIME_WORKED_{ijt} * Age40_{it} + \beta_7 TREATMENT_{jt} * TIME_WORKED_{ijt} * Age40_{it} \\
 & + \rho X_{ijt} + \varepsilon_{ijt}
 \end{aligned} \tag{5}$$

In this model, the coefficient on the triple interaction term, β_7 , represents the marginal effect of an additional unit of exposure (as measured by time worked) among employees 40 years or older who were randomized into treatment. For those under age 40, the effect of the wellness program is represented by $\beta_1 + \beta_4 * Exposure$. For those over age 40, the effect of the wellness program is represented by $\beta_1 + \beta_4 * Exposure + \beta_5 + \beta_7 * Exposure$, or $(\beta_1 + \beta_5) + (\beta_4 + \beta_7) * Exposure$. The average effects for each group can be derived by evaluating this at the average level of exposure. We will evaluate whether any differences are statistically significant.

E. Worksite-level analyses

We complement our analyses at the individual level with analyses at the worksite level. Worksite-level data were generated by aggregating values for individuals up to their initial worksite. This aggregation was weighted by the number of hours each employee worked during the treatment period. The estimating equation below captures the framework of the worksite-level analyses.

$$Y_{kt} = \beta_0 + \beta_1 TREATMENT_{kt} + \beta_2 X_{kt} + \varepsilon_{kt} \tag{6}$$

In equation (6), the subscript k denotes a worksite. Analogous to the individual-level analyses, Y_{kt} represents an outcome for worksite k at time t . $TREATMENT_{kt}$ is a binary indicator of

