randomization into treatment or control, with β_1 indicating the average worksite-level effect of being randomized into treatment. The vector of covariates X_{kt} comprises the same set of observable characteristics for individuals, aggregated to the worksite level using weighted averages (generating percentages for binary variables). The worksite-level regressions are weighted by worksite size, as measured by the total hours worked by all employees at a worksite, with standard errors adjusted for heteroscedasticity. For estimates of program effect that are significant in the individual-level analysis, we will produce parallel LATE estimates at the workplace level, analogously using treatment status as an instrument for participation.

Although the employees at each worksite could change over time, the worksites themselves were all stably represented in our data. However, at the 18-month mark, 5 worksites previously in the control group entered the treatment group. In our base specification, we will assess effects for the 20 worksites that were continuously treated throughout the 3-year period (omitting the additional 5 from the analysis altogether). As an alternative specification, we will also evaluate effects at the worksite level when considering the 5 additional worksites in the treatment group.

F. Sensitivity analyses

We conduct several types of sensitivity analyses. First, in the statistical analyses above, our base regression models use linear regression even for binary outcomes. The OLS estimator has been shown to perform better than other non-linear approaches in estimating the average population effect, particularly with large samples.¹⁰ However, OLS also has limitations, such as its sensitivity to outliers. To test the robustness of our main results to changes in functional form, we will fit logit models for binary outcome variables.

Second, we will present LATE results with alternative definitions of participation. As defined above, these include a binary indicator of participation based on completing at least one module, and a high participation indicator defined as completing at least 3 modules.

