Employee Demographics					
Age (yrs)	38.5	37.6	38.1	0.165	0.458
Female (%)	48.3	46.6	45.7	0.348	0.065
Race (%)					
Black	17.6	19.4	20.4	0.723	0.463
White	65.6	60.0	57.2	0.427	0.098
Hispanic	11.4	16.1	16.6	0.321	0.150
Other	5.5	4.4	5.8	0.295	0.665
County-Level Demographics					
Age (yrs)	40.0	39.8	39.7	0.798	0.725
Female (%)	51.1	51.4	51.3	0.183	0.228
Race (%)					
Black	12.4	12.8	13.3	0.909	0.725
White	75.9	76.9	74.7	0.773	0.687
Hispanic	11.0	14.3	13.7	0.341	0.170
Other	11.7	10.2	12.0	0.396	0.833

Notes: Demographic characteristics are plausibly unaffected by the treatment. Employee demographics are taken from the Team Member database supplied by BJ's and based on the first entry for an individual during the treatment period. Age is defined as of December, 2014 (pre-treatment). ACS demographics are taken from the 2015 American Community Survey (ACS) Population Estimates for the county each worksite is located in. Worksite-level analyses are obtained by first calculating a weighted average for each worksite (weighted by an employee's hours worked during the treatment period). Column 1 reports the means for employees in the treatment group while columns 2 and 3 report the means for the primary control employees and all control employees (primary and secondary), respectively. Treatment status is defined by the first worksite an employee appears in during the treatment period. Column 4 reports the p-value for the comparison between the employees at treatment worksites and the employees at primary control worksites and column 5 reports the p-value for the comparison between the employees at treatment worksites and all employees at control worksites.

Table 10: First Stage Estimates

Panel A: Employee Level—All

	All		Completed PHA		Cigna Enrolled	
	(1) Control Mean	(2) Estimated First Stage	(3) Control Mean	(4) Estimated First Stage	(5) Control Means	(6) Estimated First Stage
Completed any module (%)	0.21	27.53 (1.25) [0.00]	2.29	63.06 (1.98) [0.00]	0.91	57.31 (2.81) [0.00]
Modules completed (#)	0.01	1.12 (0.09) [0.00]	0.08	3.45 (0.24) [0.00]	0.03	3.13 (0.26) [0.00]
3 or more modules (%)	0.12	15.95 (1.08) [0.00]	1.60	46.74 (2.31) [0.00]	0.53	43.29 (2.74) [0.00]
Average total incentive payment (\$)	0.26	37.97 (3.20) [0.00]	3.20	126.54 (9.40) [0.00]	1.37	148.83 (11.93) [0.00]
N	41,376	48,664	1,454	2,793	7,174	8,559

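### Equation (6) adjusts for worksite covariates built from the 2015–2017 workforce and its treatment-period hours, so the worksite model conditions on a workforce mix measured after randomization

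*Combined protocol and SAP*

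**What the plan says.** Section VI.E collapses individual records to each person's initial worksite and states that "This aggregation was weighted by the number of hours each employee worked during the treatment period". The covariates in equation (6) then follow: the vector "comprises the same set of observable characteristics for individuals, aggregated to the worksite level using weighted averages". That sentence does not name the weight, but the note to Table 9 does for the demographics: "calculating a weighted average for each worksite (weighted by an employee's hours worked during the treatment period". The regression itself also uses treatment-period hours: "The worksite-level regressions are weighted by worksite size, as measured by the total hours worked by all employees at a worksite".

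The people averaged are the main sample of section V.A, which takes in anyone who worked at the company "for any length of time during the study period". The note to Table 10 Panel C adds one more worksite covariate to the first stage, the percentage of workers ever covered by Cigna during the treatment period.

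Section VI.C concedes that "to the extent that the wellness program affected hiring or tenure of employees, their presence in the data set may be endogenously determined", and adds: "Indeed, tenure and time worked are among our primary outcomes". Section V.B checks balance on job characteristics only in the stably employed subsample, because those workers had "characteristics defined prior to the intervention and thus exogenous to the treatment status". Section VI.A likewise gives a baseline date for the employment covariates only in that subsample.

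**The concern.** A site's share of staff who are over 40, part-time or in sales depends on who joined, who stayed and how many hours each person worked in 2015–2017. The plan treats these as possible effects of the program. Conditioning on them can bias the treatment coefficient in equation (6), which section VI.E defines as the average worksite-level effect of being randomized into treatment.

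If the program alters the mix and the mix predicts the outcome, adjustment removes that path. If the mix and the outcome share a cause, such as retention, adjustment can move the coefficient either way.

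No stated remedy reaches this model. The stably employed subsample and the exit bounding work at individual level. Assigning people to their initial worksite deals with transfers, but not with entry, exit or changes in hours. Yet worksites are fixed units, so a pre-intervention value can be defined for each one.

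**Working it through.** **1. How many covariates are involved.** From the list in section VI.A: 5 age + 1 sex + 5 age-by-sex + 3 race = 14 demographic terms, plus 1 full-time + 1 hourly + 2 job-type = 4 employment terms, 18 in all. The Table 10 Panel C first stage adds the Cigna share.

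**2. Turnover behind the averages.**
- Employees per club over the study: (7,288 + 41,376)/160 = 48,664/160 = 304.15. This reproduces the 304 in Figure 2.
- Section III gives 118 present at any time: 304.15/118 = 2.58 people per position.
- Stably employed share (Table 8 Panel D): (2,344 + 13,000)/48,664 = 31.5%.
- Appendix 2: 51% of the control stable sample remained at the end of December 2017.

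A person's age, sex and race are fixed with respect to the program, but with this turnover a site's hours-weighted mix is not.

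**3. What hours weighting does.** From Table 8 Panel A.1 (headcount) to Table 9 (hours-weighted site means), control age goes from 33.0 to 38.1 and control white share from 48.8% to 57.2%. In Table 2, part-time hourly goes from 57.9% to 39.5%. Treatment-minus-control gaps:

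| | Table 8 A.1 | Table 9 |
|---|---|---|
| Age (years) | 0.5 | 0.4 |
| White (points) | 8.9 | 8.4 |
| Female (points) | 1.3 | 2.6 |
| Black (points) | −5.6 | −2.8 |
| Hispanic (points) | −3.5 | −5.2 |

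These changes may be chance or the effect of site weighting. They are not evidence of a program effect.

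**4. Spending illustration.** The shift sizes are assumptions. The Table 11 control gap by age is 6,323.57 − 2,627.73 = $3,695.84. Composition effect = gap × shift in the hours share aged 40 and over, set against the worksite control mean of $5,044.74 (Table 4). Table 11 is per insured employee and the worksite mean is per 2,000 hours, so the scale is approximate.

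| Shift | Effect | % of mean | Simulated, baseline covariate | Simulated, hours-weighted covariate |
|---|---|---|---|---|
| 0 | $0 | 0 | $2 | $2 |
| 1 point | $37 | 0.7 | $39 | $2 |
| 3 points | $111 | 2.2 | $107 | −$4 |
| 5 points | $185 | 3.7 | $178 | −$7 |

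The simulation had 160 sites with 25 treated and 2,000 runs. Assumed inputs were a site share with mean 0.45 and SD 0.08, drift SD 0.03, residual spending SD $900 and no direct effect on spending. The baseline covariate leaves the composition effect in the coefficient; the treatment-period covariate removes it.

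**5. Scale.** Unadjusted, equally weighted SE for 20 v 135 sites, using the Table 4 worksite SD: 2,994.54 × √(1/20 + 1/135) = $717. Then 37/717 = 0.05 and 185/717 = 0.26. Covariate adjustment would lower this SE somewhat. For tenure (Table 3 SD 4.35): 4.35 × √(1/20 + 1/135) = 1.04 points.

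**6. Direction, for retention.** A second simulation assumed 155 sites with 20 treated, 118 refilled positions per site, 36 months, monthly exit of 9% under age 30 and 2.5% above, and 65% of hires under 30. The ratio of adjusted to unadjusted effect, using the treatment-period under-30 share, was 1.33 when a 10% cut in exit applied only to the young and 0.69 when it applied only to older staff. A uniform 10% cut gave 1–2% distortion. The baseline share gave 0.98–1.01. Other assumed settings (site hazard SD 10–20%) gave 2–7% attenuation.

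**The case against.** **The worksite model is a complement.** A reader might infer that it is offered as the check immune to entry and exit, so that this choice defeats its purpose. The documents do not say that. Section VI.E presents it alongside the individual analyses, and section VI.A calls it informative because treatment is delivered by site and has fixed costs. The stated defences against entry and exit lie elsewhere (sections V.A and VI.C). The exit-balance tests by subgroup also cover part of the mechanism, though not the mix of new hires. This stands and limits the weight of the point.

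**Nothing shows that the mix moved.** A reader might take the drop in part-time share from 57.9% to 39.5% as evidence of distortion. Table 2 covers control sites only and compares headcount with hours weighting, so it cannot show a program effect. Table 9 dates age at December 2014 and regards demographics as plausibly unaffected by treatment. That is sound for persons, but leaves the site mix open.

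**The better covariate depends on the question.** For spending or absenteeism, a program-induced change in workforce mix may be seen as selection rather than effect, and the present covariates remove it. This is a fair reason to keep that version as a secondary analysis. It does not suit a coefficient defined as the effect of randomization, and least of all tenure.

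**The repair is partial and the bias looks small.** Both stand. Outcome aggregation and regression weights also use treatment-period hours, and no conclusion is shown to change.

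**Conclusion.** The point holds as a matter of construction: equation (6) adjusts for a post-randomization site mix, contrary to the reasoning in sections V.B and VI.C, and no worksite-level remedy is stated. Whether any bias results, and in which direction, cannot be known from the documents.

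For spending, assumed shifts of 1 to 5 points give at most about a quarter of a standard error. For tenure, the distortion depends on who is retained: 1–2% under a uniform change, about 30% either way if only one age group responds. For an effect of 2.8 SE (80% power, two-sided 5%, an assumption), 7% is 0.07 × 2.8 = 0.2 SE and 31% is 0.31 × 2.8 = 0.87 SE. The latter needs both a one-sided response and a tenure effect near 2.8 × 1.04 = 2.9 points. None of these percentages is a bound.

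This should be corrected because it is cheap and removes an avoidable ambiguity. It is not a reason to distrust the individual-level analyses.

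**What to change.** 1. In the base specification of equation (6), build every covariate, including the Cigna share, from each site's pre-intervention roster: headcount on 31 December 2014, or 2014 hours. Use the same values in the worksite 2SLS, both stages, and in the Table 9 balance check.
2. Keep the present hours-weighted covariates as a named sensitivity analysis, described as the effect net of workforce composition.
3. State that outcome aggregation and regression weights still use treatment-period hours, so step 1 removes only the covariate part of the dependence. Add a sensitivity analysis with the regression weighted by 2014 site hours.

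Cost: SAP wording and re-aggregation of data that appear to be held already. Appendix 2 follows employment from 1/1/2014, and Table 8 Panel D reports 2014 Cigna enrollment. That pay-period hours also reach back through 2014 is an assumption. If they do not, headcount serves for step 1, and the weights in step 3 would need a headcount substitute.

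Downsides: baseline mix may predict 36-month outcomes slightly less well, with some loss of precision. For spending and absenteeism the coefficient will include any program-induced change in workforce mix, which the report should say.

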Administrative data consist of employment records and medical and pharmaceutical claims data. Employment records are available for all employees across treatment and control worksites (both primary and secondary controls). Medical and pharmaceutical claims data are available through Cigna for BJ's employees who are insured through a Cigna plan. In cross-section, approximately 37 percent of all BJ's employees were insured through Cigna during June 2016 (the midpoint of phase 2). Of note, BJ's as an organization is self-insured (i.e. it bears risk of health care spending of its enrolled members), with Cigna as the administrator of its health plans. We used all administrative data available for the entire study period.

A1. Employment records

BJ's provided us with data from their earnings database, which includes data elements that we use both to define our sample (based on hire and termination dates) and to measure key outcomes, such as absenteeism and performance reviews. Information included:

- **Dates and location of employment actions:** Dates and sites of hire, rehire, termination, transfer, and performance review. These data capture employment history across clubs. A small proportion of employees (4.5%) appeared in more than 1 worksite during the study period. We defined these workers' treatment or control assignment using the randomized assignment of their initial worksite, as the decision to leave (or stay) at a worksite could be endogenous. Most employees have one performance review per calendar year.
- **Demographic characteristics:** Characteristics of the working population include age, sex, and race. These are discussed in greater in the section on Analysis below. Worksite level analyses, as described below, were augmented using 2015 estimates of county-level demographic characteristics from the U.S. Census Bureau matched to the locations of each worksite.
- **Employment characteristics:** Characteristics of an individual's job include type of hired arrangement (full time salaried, full time hourly, and part time hourly) and type of job. The types of jobs were grouped into three categories: sales, non-sales (including laborers and helpers, operatives, and service workers), and other (including administrative support, craft workers, and first/mid-level office professionals).

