In this representative estimating equation, Y_{ijt} denotes an outcome of interest, such as medical spending, for individual i who is employed in worksite j at time t . $TREATMENT_{jt}$ is a binary indicator of whether the individual's worksite was randomized into treatment or control. We assigned each individual to the worksite at which he or she was employed when the treatment began in January 2015. $TIME_WORKED_{ijt}$ is the share of total available work hours in the study period that the individual actually worked; it is expressed in percentage terms. The effect of randomization to a treatment worksite is allowed to vary based on exposure to the treatment (measured via time worked during the treatment period). The treatment effect is captured by $\beta_1 + \beta_3 * Exposure$. The average effect of randomization into the treatment group can be summarized by assessing this at the average level of exposure. While we will produce estimates of the average effect of randomization into treatment, as captured in the layout of Tables 3-6, we will additionally show results for both β_1 and β_3 for each of our results in a set of parallel tables.

X_{ijt} represents a vector of covariates that may help improve precision as well as account for chance differences in characteristics between treatment and control groups, including:

- Age indicators: <20 years (omitted), 20-29, 30-39, 40-49, 50-59, and 60 and greater.
- Sex indicator: male (omitted), female
- Age-sex interactions
- Race: white (omitted), black, Hispanic, and other
- Employment characteristics (measured at baseline for the stably employed subsample):
 - Part-time (omitted), full-time
 - Salaried (omitted), hourly
 - Sales worker (omitted), non-sales worker, and other worker.

ε_{ijt} is the idiosyncratic error term. The models are weighted using the sample weights described above. Standard errors were clustered at the worksite level.

B. Local average treatment effect (LATE)

While our ITT analysis explores the effect of being randomized into a treatment worksite, a related but distinct question is: what is the effect of participating in the wellness program on the outcomes of interest? The answer to this second question will be different if not all employees in treatment worksites elect to participate. Because the choice to participate in the program is endogenous, simply including participation as a right-hand side variable may produce biased

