Notes: Table reports the coefficient on TREATMENT from estimating equation (1) by OLS (column 2), and the coefficient on PARTICIPATION from estimating equation (2) by IV (column 3). Standard errors are listed in parentheses. Column 1 reports the mean of each employment outcome in the control group for each sample (with standard deviation in parentheses, followed by the number of observations for each outcome). All regressions will include demographic and employment controls (age, sex, age-sex interactions, race/ethnicity, Cigna coverage status, full-time status, paid hourly status, and job category) and cluster standard errors at the worksite (for employee-level regressions). Employee-level and stably employed subsample control means are weighted by a weight that balances treatment and control on demographic characteristics. Worksite-level control means are not traditionally weighted: individual-level records are collapsed at the worksite-level and weighted by the total number of hours worked at each worksite. For worksite level results on tenure, the outcome was defined as the percent of total days at the worksite during the study period that was worked by employees at the worksite.

§ Tenure was defined as the number of days worked during the treatment period for the employee-level mean and stably employed subsample mean; it was defined as the percent of the entire treatment period worked by employees in the worksite-level mean.

Table 4: Impact on Medical & Pharmaceutical Spending and Utilization

	Employee-level			Stably Employed Subsample			Worksite-level (per 2000 work hours)		
	Mean in Control Group (1)	Reduced Form (Linear) (2)	2SLS (Linear) (3)	Mean in Control Group (1)	Reduced Form (Linear) (2)	2SLS (Linear) (3)	Mean in Control Group (1)	Reduced Form (Linear) (2)	2SLS (Linear) (3)
Medical Spending									
Total Spending	4800.57 (18559.82)			4721.85 (19056.92)			5044.74 (2994.54)		
Medical Utilization									
Number of Office visits	3.90 (4.47)			3.95 (4.33)			4.21 (0.93)		
Number of Hospitalizations	0.09 (0.40)			0.08 (0.36)			0.08 (0.05)		
Number of ER Visits	0.28 (0.75)			0.26 (0.61)			0.27 (0.11)		
Pharmaceutical Spending									
Total Spending	1237.60 (6921.32)			1227.32 (7115.67)			1317.72 (1145.17)		
Pharmaceutical Utilization									
Number of Distinct Medications	5.49 (6.44)			5.91 (6.54)			6.00 (1.30)		
Total Medication Months	11.20 (19.31)			11.41 (19.37)			12.39 (4.38)		
N	7,174			5,779			135		

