Appendix 2. Determination of the Stably Employed Subsample

[figure not shown]
We conducted an analysis of the duration of employment (tenure), which informed our definition of the pre-specified stably employed subsample. This analysis of tenure is described below.

Figure 1A looks at a number of scenarios where we take samples of treatment (T) and control (C) workers who were employed for varying numbers of consecutive weeks starting on 1/1/2014. In each scenario, we follow the samples of workers until they reach 1/1/2015 and look at how many of them are still employed. To be precise, for each restriction criterion of the number of consecutive weeks worked starting 1/1/2014 (X axis), the height of the dark blue bar (C 14) depicts the total number of control workers in the sample and the height of the light blue bar (C 15) depicts the total number of control workers who were still working on 1/1/2015. Analogously, the height of the black bar (T 14) represents treatment workers who started in the sample on 1/1/2014 and the height of the gray bar (T 15) represents treatment workers who were still working on 1/1/2015. Of note, the bars are overlapping for each X (i.e. they are not stacked; rather they all originate at 0). The solid and dotted lines merely reflect the percentages of C and T employees, respectively, who were still working at BJ's on 1/1/2015 (i.e. light blue bar divided by dark blue bar, gray bar divided by black bar).

Thus, for example, the interpretation of the bar when X=17 is as follows. There were about 10,000 employees in control worksites who were employed at BJ’s on 1/1/2014 and who worked through the first 17 weeks of 2014 (dark blue bar). Among these employees, about 79% (or about 7,900) were still working on 1/1/2015 (light blue bar). The same retention of 79% was found among employees in treatment worksites—calculated using the gray (numerator) and black (denominator) bars. The bar originating at X=0 represents the case of no sample restrictions (i.e. all employees in the data).

[figure not shown]

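### Site-level 2014 retention, derivable for both arms, is left out of the tenure models in equations (6) and (7), which gives up some precision and protection against chance site imbalance

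*Combined protocol and SAP*

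**What the plan says.** Section VI.C gives tenure its status: "Indeed, tenure and time worked are among our primary outcomes".

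The covariates are set out in three places.
- Section VI.A lists age, sex, age by sex, race and job characteristics, the last given as "Employment characteristics (measured at baseline for the stably employed subsample").
- The note to Table 3, where tenure is reported, lists "age, sex, age-sex interactions, race/ethnicity, Cigna coverage status, full-time status, paid hourly status, and job category".
- Section VI.E says that the worksite vector "comprises the same set of observable characteristics for individuals, aggregated to the worksite level using weighted averages". Section IV.A1 adds that county demographics augment the worksite analyses; these are again demographics.

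The balance weights use age, sex and race (Section V.B). Equation (7) in Section VI.F keeps the covariate vector and drops the exposure terms. No model, weight or sensitivity analysis uses a site's earlier turnover, a site fixed effect or a before-after difference.

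The pre-program data are there. The employment records, held for all 160 worksites, include "Dates and sites of hire, rehire, termination, transfer, and performance review". Appendix 2 follows workers in both arms through 2014. For control workers in the 17-week cohort: "Among these employees, about 79% (or about 7,900) were still working on 1/1/2015". For the other arm: "The same retention of 79% was found among employees in treatment worksites". Section VI.E adds that "the worksites themselves were all stably represented in our data".

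**The concern.** Worksites were randomized, so the number of sites and the variation between them largely set the precision for tenure. The base worksite model has 20 treated sites. If some clubs keep their staff and others do not, year after year, that difference either stays in the error term or, when it falls unevenly by chance, enters the estimated effect. Demographics and job mix may capture only part of it.

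Chance geographic imbalance is not hypothetical here. Section V.B reports that Ohio and Virginia sites fell disproportionately to treatment and Florida sites to control. If turnover varies by region, a site's own 2014 retention would address this directly, and it is fixed before the program starts. At stake are a wider interval than necessary for a primary outcome, and less protection against an unlucky allocation of sites.

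**Working it through.** The plan states no sample size, power or detectable difference, so there is no design figure to reproduce. Two-sided alpha 0.05 and 80% power are assumed below.

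**Inputs**
- Worksite tenure in controls: 76.08% of the period, SD 4.35, 135 sites (Table 3). The SD is raw, before covariates.
- Employee-level tenure in controls: SD 399.87 days, n = 41,376 (Table 3). The period 2015 to 2017 has 1,096 days.
- Treated sites: 20 in the base worksite model, 25 in the alternative (Section VI.E).
- Employees per site at any one time: 118 (Section III). Per control site over the study: 41,376/135 = 306.

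**Step 1. Precision without the covariate**
- SE = 4.35 × √(1/20 + 1/135) = 1.04 points; detectable difference = 2.80 × 1.04 = 2.92.
- With 25 treated sites: SE = 4.35 × √(1/25 + 1/135) = 0.95; detectable difference 2.65.

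**Step 2. Effect of adding it.** The SE is multiplied by √(1 − ρ²), where ρ is the site-level correlation of 2014 retention with tenure after the planned covariates. The documents do not give ρ; it is assumed.

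| ρ | SE falls by | Detectable, 20 v 135 | Detectable, 25 v 135 |
|---|---|---|---|
| 0.2 | 2.0% | 2.86 | 2.60 |
| 0.3 | 4.6% | 2.79 | 2.53 |
| 0.5 | 13.4% | 2.53 | 2.30 |
| 0.6 | 20.0% | 2.34 | 2.12 |

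Power for a 2-point effect (20 v 135) is 48% without the covariate, 52% at ρ = 0.3 and 60% at ρ = 0.5.

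**Step 3. How large can ρ be?** Both measures carry sampling noise.
- Outcome: the individual SD is 399.87/1,096 = 36.5 points. With 306 equally weighted employees the noise variance is 36.5²/306 = 4.35, which is 23% of 4.35² = 18.92. Hours weighting lowers the effective number; at an illustrative 120 it is 11.1, or 59%. True site variance is then about 14.6 or 7.8.
- 2014 retention: with 118 employees and 79% to 70% retained, the noise SD is 3.7 to 4.2 points (variance 14.1 to 17.8).
- Assume the same true site SD in both periods and perfect persistence. The upper limit of ρ is then √(0.77 × 14.6/(14.6 + 14.1)) = 0.63 in the favorable case and √(0.41 × 7.8/(7.8 + 17.8)) = 0.35 in the other.
- With persistence of 0.7 these become 0.44 and 0.25, and the SE falls by 10% or 3%.

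A larger true site SD in 2014 would raise the limit; the documents give none.

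**Step 4. Equation (7), 25 v 135 sites.** The documents give no intraclass correlation (ICC). Per arm, the variance of the mean is 399.87² × [ICC × (1 − ρ²) + (1 − ICC)/m]/k, with k sites of m employees (7,288/25 = 292 treated, 306 control). At an assumed ICC of 0.01 to 0.03, the detectable difference is 28 to 45 days without the covariate and 25 to 39 days at ρ = 0.5.

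**The case against.** The strongest reply is that this is an optional gain. Randomization with clustered or robust standard errors gives valid inference without the covariate, the pooled 2014 retention is 79% in both arms, and one common covariate set for all outcomes guards against specification searching. The worksite model is described as complementing the individual analysis, and equation (7) is a sensitivity model. All of this stands, and it limits the point to precision and chance imbalance. It does not remove the point: the 79% is an arm-level figure for one cohort and says nothing about variation between sites or about the 20-site base comparison. A covariate named before the arms are compared is not specification searching.

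A reader might infer more than the documents support:
- **That the estimate is biased.** Nothing shows this.
- **That power would rise from 80% to about 90% or 97%.** Those figures need ρ of 0.5 or 0.7. Under Step 3's assumptions 0.5 is optimistic and 0.7 exceeds the limit. Aggregated age and job mix may also already absorb some persistent turnover.
- **That 2014 retention is the baseline value of the outcome.** Worksite tenure is an hours-weighted percentage of the period worked and includes new hires; retention of those employed on 1/1/2014 is related but different.
- **That site values are already tabulated.** They can be derived from the records, but only pooled values are shown.
- **That equation (1) needs the same change.** It already contains TIME_WORKED, measured after randomization and close to a proxy for tenure. That is a separate problem, to be settled first.

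**Conclusion.** The point holds as a modest, inexpensive improvement to the tenure analyses in equations (6) and (7). The adjustment is absent from the plan, the data to build it exist for both arms, and the outcome is named as primary. With the raw SD of 4.35 and 20 v 135 sites, the SE of 1.04 points would fall by about 2% to 20% over an assumed partial correlation of 0.2 to 0.6, and by about 5% to 13% at 0.3 to 0.5. At the low end the gain is small. The size rests on persistence of site turnover from 2014 to 2015–17, which the documents do not report, and on a raw SD that the planned covariates may reduce. Validity of inference is not in question.

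**What to change.** Before the arms are compared on three-year outcomes:
- Pre-specify site-level 2014 retention as a covariate for tenure in equation (6), in its parallel worksite LATE (both stages), and in equation (7). Define it as the share of those employed on 1/1/2014 who were still employed on 1/1/2015, by initial worksite. A 2014 hours-weighted measure built like the outcome would also serve.
- First reconcile the two definitions of tenure: Section IV.A1 runs from hire to latest termination, while Table 3 uses days worked, or percent of the period, within the treatment period.
- Show the covariate's balance by arm in Table 9.
- Report the tenure model without it as a sensitivity analysis.
- Settle the use of TIME_WORKED as a regressor for tenure before adding the covariate to equation (1).

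The cost is some SAP wording, one variable derived from records already held, one degree of freedom among 155 to 160 worksites, and a covariate set that differs for one outcome.
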